Appendix 2: Common Terminology Criteria for Adverse Events V4.0 (CTCAE)

The descriptions and grading scales found in the revised NCI Common Terminology Criteria for Adverse Events (CTCAE) version 4.0 will be utilized for adverse event reporting. (<http://ctep.cancer.gov/reporting/ctc.html>)

A Phase II, Single-arm Study of Combination Pembrolizumab and Olaparib in the Treatment of Patients with Advanced Cholangiocarcinoma

Version 2.1: 17Mar2023

Appendix 3: Contraceptive Guidance and Pregnancy Testing

Woman of Childbearing Potential (WOCBP)

A woman is considered fertile following menarche and until becoming post-menopausal unless permanently sterile (see below)

Women in the following categories are not considered WOCBP:

- Premenarchal
- Premenopausal female with 1 of the following:
 - Documented hysterectomy
 - Documented bilateral salpingectomy
 - Documented bilateral oophorectomy

Note: Documentation can come from the site personnel's review of the participant's medical records, medical examination, or medical history interview.

- Postmenopausal female
 - A postmenopausal state is defined as no menses for 12 months without an alternative medical cause.
 - A high follicle stimulating hormone (FSH) level in the postmenopausal range may be used to confirm a postmenopausal state in women not using hormonal contraception or hormonal replacement therapy (HRT). However, in the absence of 12 months of amenorrhea, confirmation with two FSH measurements in the postmenopausal range is required.
 - Females on HRT and whose menopausal status is in doubt will be required to use one of the non-hormonal highly effective contraception methods if they wish to continue their HRT during the study. Otherwise, they must discontinue HRT to allow confirmation of postmenopausal status before study enrollment.

Contraception Requirements

Male Participants:

Male participants with female partners of childbearing potential are eligible to participate if they agree to one of the following during the protocol-defined time frame in section X:

- Be abstinent from penile-vaginal intercourse as their usual and preferred lifestyle (abstinent on a long term and persistent basis) and agree to remain abstinent
- Use a male condom plus partner use of a contraceptive method with a failure rate of <1% per year as described in Table 9 when having penile-vaginal intercourse with a woman of childbearing potential who is not currently pregnant.
 - Note: Men with a pregnant or breastfeeding partner must agree to remain abstinent from penile-vaginal intercourse or use a male condom during each episode of penile penetration.

A Phase II, Single-arm Study of Combination Pembrolizumab and Olaparib in the Treatment of

Patients with Advanced Cholangiocarcinoma

Version 2.1: 17Mar2023

Female Participants:

Female participants of childbearing potential are eligible to participate if they agree to use a highly effective method of contraception that has a low user dependency consistently and correctly as described in Table 9 during the protocol-defined time frame in Section X.

Female Participants:

Female participants of childbearing potential are eligible to participate if they agree to use a highly effective method of contraception consistently and correctly as described in Table 10 during the protocol-defined time frame in Section X.

Table 10 Highly Effective Contraception Methods

Highly Effective Contraceptive Methods That Are User Dependent ^a Failure rate of <1% per year when used consistently and correctly.

● Combined (estrogen- and progestogen- containing) hormonal contraception ^{b, c}
○ Oral○ Intravaginal○ Transdermal○ Injectable● Progestogen-only hormonal contraception ^{b, c}
○ Oral○ Injectable
Highly Effective Methods That Have Low User Dependency Failure rate of <1% per year when used consistently and correctly.

● Progestogen- only contraceptive implant ^{b, c}● Intrauterine hormone-releasing system (IUS) ^b● Intrauterine device (IUD)● Bilateral tubal occlusion

● Vasectomized partner A vasectomized partner is a highly effective contraception method provided that the partner is the sole male sexual partner of the WOCBP and the absence of sperm has been confirmed. If not, an additional highly effective method of contraception should be used.● Sexual abstinence Sexual abstinence is considered a highly effective method only if defined as refraining from heterosexual intercourse during the entire period of risk associated with the study treatment. The

A Phase II, Single-arm Study of Combination Pembrolizumab and Olaparib in the Treatment of Patients with Advanced Cholangiocarcinoma

Version 2.1: 17Mar2023

reliability of sexual abstinence needs to be evaluated in relation to the duration of the study and the preferred and usual lifestyle of the participant.)

Notes:

Use should be consistent with local regulations regarding the use of contraceptive methods for participants of clinical studies.

- a) Typical use failure rates are lower than perfect-use failure rates (i.e. when used consistently and correctly).
- b) If hormonal contraception efficacy is potentially decreased due to interaction with study treatment, condoms must be used in addition to the hormonal contraception during the treatment period and for at least [X days, corresponding to time needed to eliminate study treatment plus 30 days for study treatments with genotoxic potential] after the last dose of study treatment .
- c) If locally required, in accordance with Clinical Trial Facilitation Group (CTFG) guidelines, acceptable hormonal contraceptives are limited to those that inhibit ovulation.

Pregnancy Testing

WOCBP should only be included after a negative highly sensitive urine or serum pregnancy test and in accordance with local requirements. When applicable this test should be repeated a maximum of 24-hours before the first dose/vaccination.

Following initiation of treatment additional pregnancy testing will be performed at monthly intervals during the treatment period and at [X days] after the last dose of study treatment and as required locally.

Pregnancy testing will be performed whenever an expected menstrual cycle is missed or when pregnancy is otherwise suspected.

A Phase II, Single-arm Study of Combination Pembrolizumab and Olaparib in the Treatment of Patients with Advanced Cholangiocarcinoma

Version 2.1: 17Mar2023

Appendix 4: Description of the iRECIST Process for Assessment of Disease Progression

Assessment at Screening and Prior to RECIST 1.1 Progression

Until radiographic progression based on RECIST 1.1, there is no distinct iRECIST assessment.

Assessment and Decision at RECIST 1.1 Progression

In participants who show evidence of radiological PD by RECIST 1.1 the Investigator will decide whether to continue a participant on study treatment until repeat imaging is obtained (using iRECIST for participant management (see Table 5 and Figures 1 and 3). This decision by the Investigator should be based on the participant's overall clinical condition.

Clinical stability is defined as the following:

- Absence of symptoms and signs indicating clinically significant progression of disease
- No decline in ECOG performance status
- No requirements for intensified management, including increased analgesia, radiation, or other palliative care

Any participant deemed clinically unstable should be discontinued from study treatment at site-assessed first radiologic evidence of PD, and is not required to have repeat tumor imaging for confirmation of PD by iRECIST.

If the Investigator decides to continue treatment, the participant may continue to receive study treatment and the tumor assessment should be repeated 4 to 8 weeks later to confirm PD by iRECIST, per Investigator assessment. I

Tumor flare may manifest as any factor causing radiographic progression per RECIST 1.1, including:

- Increase in the sum of diameters of target lesion(s) identified at baseline to $\geq 20\%$ and ≥ 5 mm from nadir
 - Please note: the iRECIST publication uses the terminology “sum of measurements”, but “sum of diameters” will be used in this protocol, consistent with the original RECIST 1.1 terminology.
- Unequivocal progression of non-target lesion(s) identified at baseline
- Development of new lesion(s)

iRECIST defines new response categories, including iUPD (unconfirmed progressive disease) and iCPD (confirmed progressive disease). For purposes of iRECIST assessment, the first visit showing progression according to RECIST 1.1 will be assigned a visit (overall) response of iUPD, regardless of which factors caused the progression.

A Phase II, Single-arm Study of Combination Pembrolizumab and Olaparib in the Treatment of Patients with Advanced Cholangiocarcinoma

Version 2.1: 17Mar2023

At this visit, target and non-target lesions identified at baseline by RECIST 1.1 will be assessed as usual.

New lesions will be classified as measurable or non-measurable, using the same size thresholds and rules as for baseline lesion assessment in RECIST 1.1. From measurable new lesions, up to 5 lesions total (up to 2 per organ), may be selected as New Lesions – Target. The sum of diameters of these lesions will be calculated, and kept distinct from the sum of diameters for target lesions at baseline. All other new lesions will be followed qualitatively as New Lesions – Non-target.

Assessment at the Confirmatory Imaging

On the confirmatory imaging, the participant will be classified as progression confirmed (with an overall response of iCPD), or as showing persistent unconfirmed progression (with an overall response of iUPD), or as showing disease stability or response (iSD/iPR/iCR).

Confirmation of Progression

Progression is considered confirmed, and the overall response will be iCPD, if ANY of the following occurs:

- Any of the factors that were the basis for the initial iUPD show worsening
 - For target lesions, worsening is a further increase in the sum of diameters of ≥ 5 mm, compared to any prior iUPD time point
 - For non-target lesions, worsening is any significant growth in lesions overall, compared to a prior iUPD time point; this does not have to meet the “unequivocal” standard of RECIST 1.1
 - For new lesions, worsening is any of these:
 - An increase in the new lesion sum of diameters by ≥ 5 mm from a prior iUPD time point
 - Visible growth of new non-target lesions
 - The appearance of additional new lesions
- Any new factor appears that would have triggered PD by RECIST 1.1

Persistent iUPD

Progression is considered not confirmed, and the overall response remains iUPD, if:

- None of the progression-confirming factors identified above occurs AND
- The target lesion sum of diameters (initial target lesions) remains above the initial PD threshold (by RECIST 1.1)

A Phase II, Single-arm Study of Combination Pembrolizumab and Olaparib in the Treatment of Patients with Advanced Cholangiocarcinoma

Version 2.1: 17Mar2023

Additional imaging for confirmation should be scheduled 4 to 8 weeks from the scan on which iUPD is seen. This may correspond to the next visit in the original visit schedule. The assessment of the subsequent confirmation scan proceeds in an identical manner, with possible outcomes of iCPD, iUPD, and iSD/iPR/iCR.

Resolution of iUPD

Progression is considered not confirmed, and the overall response becomes iSD/iPR/iCR, if:

- None of the progression-confirming factors identified above occurs, AND
- The target lesion sum of diameters (initial target lesions) is not above the initial PD threshold.

The response is classified as iSD or iPR (depending on the sum of diameters of the target lesions), or iCR if all lesions resolve.

In this case, the initial iUPD is considered to be pseudo-progression, and the level of suspicion for progression is “reset”. This means that the next visit that shows radiographic progression, whenever it occurs, is again classified as iUPD by iRECIST, and the confirmation process is repeated before a response of iCPD can be assigned.

Management Following the Confirmatory Imaging

If repeat imaging does not confirm PD per iRECIST, as assessed by the Investigator, and the participant continues to be clinically stable, study treatment may continue and follow the regular imaging schedule. If PD is confirmed, participants will be discontinued from study treatment.

NOTE: If a participant has confirmed radiographic progression (iCPD) as defined above, but the participant is achieving a clinically meaningful benefit, an exception to continue study treatment may be considered. In this case, if study treatment is continued, tumor imaging should continue to be performed following the intervals as outlined in Section 6.

Detection of Progression at Visits After Pseudo-progression Resolves

After resolution of pseudo-progression (i.e., achievement of iSD/iPR/iCR), iUPD is indicated by any of the following events:

- Target lesions
 - Sum of diameters reaches the PD threshold ($\geq 20\%$ and ≥ 5 mm increase from nadir) either for the first time, or after resolution of previous pseudo-progression. The nadir is always the smallest sum of diameters seen during the entire trial, either before or after an instance of pseudo-progression.
- Non-target lesions
 - If non-target lesions have never shown unequivocal progression, their doing so for the first time results in iUPD.

A Phase II, Single-arm Study of Combination Pembrolizumab and Olaparib in the Treatment of Patients with Advanced Cholangiocarcinoma

Version 2.1: 17Mar2023

- If non-target lesions had shown previous unequivocal progression, and this progression has not resolved, iUPD results from any significant further growth of non-target lesions, taken as a whole.
- New lesions
 - New lesions appear for the first time
 - Additional new lesions appear
 - Previously identified new target lesions show an increase of ≥ 5 mm in the new lesion sum of diameters, from the nadir value of that sum
 - Previously identified non-target lesions show any significant growth

If any of the events above occur, the overall response for that visit is iUPD, and the iUPD evaluation process (see Assessment at the Confirmatory Imaging above) is repeated. Progression must be confirmed before iCPD can occur.

The decision process is identical to the iUPD confirmation process for the initial PD, except in one respect. If new lesions occurred at a prior instance of iUPD, and at the confirmatory scan the burden of new lesions has increased from its smallest value (for new target lesions, their sum of diameters is ≥ 5 mm increased from its nadir), then iUPD cannot resolve to iSD or iPR. It will remain iUPD until either a decrease in the new lesion burden allows resolution to iSD or iPR, or until a confirmatory factor causes iCPD.

Additional details about iRECIST are provided in the iRECIST publication [Seymour et al, 2017].

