4.5.2 Secondary Endpoints

The secondary study endpoints are the duration of response (DOR), progression free survival (PFS), and overall survival (OS) in patients receiving the combination therapy. All of these endpoints are part of the clinical response assessment.

Primary Endpoint Definition

1. The objective response rate (ORR) is the proportion of all subjects with confirmed PR or CR according to RECIST 1.1, from the start of treatment until disease progression/recurrence (taken as reference for progressive disease, the smallest measurements recorded since the start of treatment).

Secondary Endpoint Definition

1. PFS is defined as the duration from the date of registration until disease progression (as defined above; using RECIST 1.1) or death occurs. Subjects who have not progressed will be right-censored at the date of the last disease evaluation.
2. OS is defined as the time of registration until death as a result of any cause.
3. Overall response rate (ORR) is defined as the sum of complete response (CR) + confirmed partial response (PR) and will be determined using the immune-related response criteria (iRECIST).
4. Grade 3 and 4 toxicities as defined by the NCI Common Terminology Criteria for Adverse Events (NCI CTCAE) v4.

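### Under Appendix 4, an iUPD triggered only by a new or non-target lesion cannot remain iUPD, so a patient whose trigger lesion persists can count as a confirmed iPR in the secondary iRECIST ORR

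*Combined protocol and SAP*

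**What the plan says.** Appendix 4 lists three routes to RECIST 1.1 progression: growth of the target lesions, unequivocal progression of non-target lesions, and new lesions. The first visit showing any of them "will be assigned a visit (overall) response of iUPD, regardless of which factors caused the progression".

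At the repeat scan, progression is confirmed (iCPD) by any of the following: a further rise of at least 5 mm in the target sum, any significant non-target growth, a rise of at least 5 mm in the new-lesion sum, "Visible growth of new non-target lesions", additional new lesions, or a new factor that would itself be RECIST 1.1 progression. If none of these occurs, the status depends on one quantity:

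- It stays iUPD if "The target lesion sum of diameters (initial target lesions) remains above the initial PD threshold (by RECIST 1.1").
- It resolves if "The target lesion sum of diameters (initial target lesions) is not above the initial PD threshold".

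After resolution the category is iSD or iPR according to the target sum, or iCR if every lesion has gone. The iUPD is then regarded as pseudo-progression.

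Of the measurable new lesions, "up to 5 lesions total (up to 2 per organ), may be selected as New Lesions" to be followed as target. All other new lesions are followed qualitatively as non-target.

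On the endpoint, Section 4.5.2, secondary item 3, reads "Overall response rate (ORR) is defined as the sum of complete response (CR) + confirmed partial response (PR") and names iRECIST. Section 8.1.1.2 item 2c names irRC for the corresponding endpoint and does not say that the response must be confirmed. Section 7.1.2.6.2 asks for a confirming scan at least 4 weeks after a response is first seen.

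**The concern.** Three kinds of event can start an iUPD, but the test that separates staying iUPD from resolving looks only at the initial target lesions. For two of the three triggers, that test says nothing about the lesion that caused the iUPD. A new metastasis that is still there is then classified in the same way as one that has disappeared, unless every lesion has gone.

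The secondary ORR is at stake. iRECIST departs from RECIST 1.1 only after RECIST 1.1 progression, so relative to the RECIST 1.1 rate this route can only add responders. Adding true late responders is the purpose of the endpoint. Adding patients whose progression has neither worsened nor resolved is not.

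The trial is open-label with a single arm, and the investigator makes the iRECIST assessment (Section 7.1.2.6.6). An optional choice about how to list a new lesion can also change the result.

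**Working it through.** The plan gives no figure to reproduce here, so the check is of the rule itself, followed by arithmetic on its size.

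**1. Can a patient stay iUPD?** Take an iUPD caused only by a new or non-target lesion. By construction the target sum is not above the PD threshold, so it cannot remain above it. If it crosses the threshold at the repeat scan, that is a new progression factor and gives iCPD. Persistent iUPD is therefore out of reach.

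**2. Outcomes at the first repeat scan** (iUPD from a new target lesion only, target sum below the PD threshold, other lesions still present):

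| New lesion at repeat scan | Target sum not PR | Target sum PR |
|---|---|---|
| Grown by 5 mm or more, or additional new lesions | iCPD | iCPD |
| Grown by less than 5 mm | iSD | iPR |
| Unchanged | iSD | iPR |
| Shrunk but present | iSD | iPR |
| Gone | iSD | iPR |

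The last four rows are identical. iCR is not possible while any lesion persists. Appendix 4 is consistent with this reading: its rules for visits after resolution cover the case "If non-target lesions had shown previous unequivocal progression, and this progression has not resolved".

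**3. Can a growing lesion pass?** All inputs in this step are assumed: targets down 35% and classed as PR (the documents give no numeric PR threshold), a new 15 mm lesion first seen at week 6 and listed as target, volume doubling time T = 10 weeks, and no other worsening.

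- Diameter t weeks after first detection: d(t) = d0 × 2^(t/(3T)).
- Week 12 (t=6): 15 × 2^0.2 = 17.2 mm.
- Week 18 (t=12): 15 × 2^0.4 = 19.8 mm, a rise of 4.8 mm (32%).

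The 5 mm limit is not reached, so there is no iCPD. It is not reached from the nadir either, so there is no new iUPD. The patient is iPR at weeks 12 and 18, which are 6 weeks apart, and so is a confirmed iPR.

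A 15 mm lesion reaches +5 mm by time t only if T ≤ t/(3 × log2(20/15)). That is 4.8 weeks at t=6 and 9.6 weeks at t=12, so the example lies just beyond the limit for two scans. Had the same lesion been listed as non-target, visible growth would have been enough for iCPD.

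**4. Effect on the secondary ORR.** One patient is 1/33 = 3.0 points, or 1/36 = 2.8 points. As an illustration with assumed counts and exact 95% intervals:

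- 8/33 = 24.2% (11.1 to 42.3)
- 9/33 = 27.3% (13.3 to 45.5)
- 10/33 = 30.3% (15.6 to 48.7)

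The number of such patients is not in the documents. An assumed 0 to 3 gives 0 to 3/33 = 9.1 points.

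**The case against.** The strongest reply is that the rule is permissive but complete. Every state receives a category, and resolution has two conditions joined by AND. A reader might infer that the target sum alone resolves an iUPD. It does not: defined new-lesion growth, additional new lesions, significant non-target growth or a new progression factor each gives iCPD first. That stands. The point is limited to trigger lesions that do not meet a worsening criterion, although for new target lesions this includes growth below 5 mm.

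A reader might also infer that Appendix 4 admits a gap, because at a later episode a raised new-lesion burden blocks resolution: "It will remain iUPD until either a decrease in the new lesion burden allows resolution to iSD or iPR". The text does not support this. At the first repeat scan the smallest burden of the new target lesions is the one at first iUPD, so a 5 mm rise is already iCPD. The block matters only after a reset, and it never stops a stable lesion.

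Nor can Appendix 4 be called a misstatement of the iRECIST publication that it cites. The documents do not reproduce that publication, and asking that the trigger be gone is an analytic choice.

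The effect is also limited. The primary ORR and PFS use RECIST 1.1. The immune-criteria ORR has an exact interval and no test, and Section 8.2.2 appears to call it exploratory. Because Section 8.1.1.2 says irRC, it is not settled that Appendix 4 governs this endpoint, although it is the only immune-response algorithm set out in the documents. All of this stands. It limits the weight of the point without removing it.

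**Conclusion.** The point holds as a limited one. Once no confirming factor is present, only the initial target sum separates persistent iUPD from resolution. An iUPD triggered solely by a new or non-target lesion therefore ends as iCPD, or as iSD or iPR with the label of pseudo-progression (iCR only if every lesion has gone). A patient whose trigger lesion persists can become a confirmed iPR.

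The size is 3.0 points per patient at n=33 (2.8 at n=36). This applies only to patients who were not confirmed responders before progression; the others add nothing. It also requires a patient kept under iRECIST assessment after first progression, with a target response and no other worsening. The total may be zero.

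A reader might infer that the trial's go/no-go decision is affected. It is not, because that decision rests on the RECIST 1.1 response rate. The conclusion assumes that the secondary ORR is to be read under Appendix 4, as Section 4.5.2 says.

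**What to change.** 1. Reconcile Section 4.5.2 item 3 (iRECIST, confirmed) with Section 8.1.1.2 item 2c (irRC, confirmation not stated).
2. In both places, count an iPR after an iUPD as a response only if the new or non-target lesion that triggered the iUPD is no longer present as progression, and define that state. Report beside it the ORR under the present Appendix 4 wording, and list the patients who differ.
3. Record at the first iUPD scan, before the repeat scan, which new lesions are followed as target and which as non-target, because the worsening thresholds differ.

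This uses scans already planned. The cost is one more tabulation, one recorded item per iUPD and possibly a slightly lower secondary ORR.

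Two broader changes have side effects. Making target selection compulsory would move measurable new lesions, up to the cap, from the visible-growth criterion to the looser 5 mm limit. Keeping these patients at iUPD for all purposes would affect repeat imaging and treatment, because the imaging and treatment table in Section 7.1.2.6.6 depends on the category. The change proposed here is to endpoint counting only. Any link between iUPD status and imaging or treatment is for the sponsor to reconcile, and no treatment rule is proposed.
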